# **Definitions**

## Baseline

For all parameters, baseline will be defined as the last available data point just prior to the first treatment, which occurs at visit 3.

## Visit window data including study endpoints

For each weekly visit a window of  $\pm 2$  days will be adopted for data.

## Healing of Index Ulcer

Healing is defined as complete epithelialization of the ulcer without drainage observed in the index ulcer.

# Date of healing

The date of healing is defined as the date of the first assessment of index ulcer healing.

# Days to Index Ulcer healing

For subjects who achieve healing of index ulcer during the Treatment Phase, days to healing of Index Ulcer will be calculated. Time to first assessment of ulcer healing will be used for this time-to-event analysis.\*

For the right censored subjects (i.e., subjects who do not have a wound healing event) the time to heal in days will be:

- 42 days if the subject completes the study
- Time of the early termination date of randomization for those subjects who withdraw or terminate early from the study (i.e. the censored time)

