#### Statistical methodology

#### Missing data

\*For calculation purposes, days to healing = date ulcer is first healed – date of randomization.

SAP: LLA-Nu3-CLIN002 Page 6 of 21

Missing data may be the result of missed visits, subjects lost to follow-up or who have died, and may be endpoint data or covariate data. Missing continuous outcome data will be imputed in this study using the LOCF (last observation carried forward). If wound healing outcomes are missing these will be imputed as follows: (a) If an event removes the index ulcer, such as an amputation, the outcome will be scored as not healed; (b) If a subject dies, the outcome will be scored as not healed; (c) If a subject is withdrawn from the study, the outcome will be scored as not healed; and (d) for all remaining non-healed index ulcers in the drug groups, the outcomes will be based on non-right-censored outcomes in the SOC group to weight outcomes.

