  - Laboratory evaluations and vital signs assessments will be summarized by dose group (including placebo group) and time point of collection (i.e., visit number starting with randomization visit) (see shell Table 2).
    - Tables will also be constructed for each subject per timeline (see Shell Table 3)

[figure not shown]
SAP: LLA-Nu3-CLIN002 Page 8 of 21

 Table describing change in value and percentage change from baseline for each visit will be provided for vital signs for each subject (see Shell Table 4)

- Table describing out-of-normal range shifts will be provided for clinical laboratory results for each subject, grouped according to dose group (See Shell Table 5)
- Table describing changes noted in physical examinations (at each visit after randomization) will be constructed for each subject, grouped according to dose group (see Shell Table 6)
- Efficacy date will be analyzed as follows:
  - Summary statistics of DFUs that healed by treatment group by 6 weeks (numbers and percentage healed); graph showing weekly percentage of wounds healed by treatment group
  - PAR weekly plot by treatment group; summary table of PAR values by week and treatment group
  - Time to heal within 6 weeks (summary time to heal statistics by treatment group) using Kaplan-Meier method; probability of wound healing (1-survival ≡ 1-wounds not healed) plot by treatment group. If the percentage healed figures for the 5% and 10% Nu-3 groups at 6 weeks is within 10% and a statistical power calculation shows that the proportions of wounds healed for the combined versus placebo groups is at least 80%, the times to heal will be tested using the logrank test.
  - Bacterial counts (CFU/g) for weeks 0-4 will be analyzed by (a) reporting the means and standard deviations for each group at each time point and (b) using GLMM (general linear modeling with repeated measures [weeks 1-4] and counts at week 0 as a factor)
  - Microbiological data will be summarized for each of the 3 treatment groups for each visit (visits 1, 3, 4, 5, 6, 7; unscheduled visit; early termination) as follows (a) list of species detected in each microbiological sample (Shell Table 11); and (b) susceptibility testing to the following drugs for each microbiological sample: penicillin, vancomycin, and linezolid (Shell Table 12)
    - \*A reason will be given in each instance in which susceptibility testing was *not* done (e.g., no growth).

SAP: LLA-Nu3-CLIN002 Page 9 of 21

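### The SAP does not say whether Visit 8 healings count in its six-week Kaplan-Meier curve, and it times healing and censoring on different scales

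*SAP*

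**What the plan says.** **Which healings are events.** The SAP section on days to index ulcer healing states: "For subjects who achieve healing of index ulcer during the Treatment Phase, days to healing of Index Ulcer will be calculated". The protocol synopsis (duration) gives treatment as 28 days. The same SAP section defines right-censored subjects as "subjects who do not have a wound healing event" and sets their time at "42 days if the subject completes the study". Subjects who leave early are censored at their early termination date.

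**The time scale.** "The date of healing is defined as the date of the first assessment of index ulcer healing". The footnote on the calculation starts from "days to healing = date ulcer is first healed" and subtracts the randomization date, so event times are actual dates.

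**The planned outputs.** The SAP's Analysis section lists "Summary statistics of DFUs that healed by treatment group by 6 weeks" and "Time to heal within 6 weeks (summary time to heal statistics by treatment group) using Kaplan-Meier method", with a plot of the probability of healing. A log-rank test follows only if set conditions are met.

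**Visit 8.** Protocol Section 8 allows two days either side of Day 42 after randomization, that is Days 40 to 44, and has the ulcer examined there.

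**28 days or six weeks.** The protocol points both ways. Its objectives table (synopsis and Section 4) sets endpoints at 28 days, and Section 8 makes Visit 7 the last efficacy assessment. Against that, Section 5.5 says Visit 8 evaluates the ulcer as well as safety, and the SAP's healing outputs run to six weeks.

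**The concern.** A Kaplan-Meier curve needs one rule for what counts as an event and one clock for events and censorings. The SAP has neither for its six-week curve.

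First, events appear to stop at 28 days while follow-up time runs to 42. Applied literally, a subject first seen healed at Visit 8 is either censored at 42 days, as a completer without an event, or has no defined time. The curve then does not show six-week healing.

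Second, if Visit 8 healings do count, their times can be 43 or 44 days while every non-healed completer is removed at 42. A late healing is then divided by a risk set that no longer contains the subjects it should be compared with.

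With arms of 12, 12 and 8, one subject's visit date can change the end of a curve and its median. If the choice is left until the data are seen, the analyst must pick among rules that give very different figures for the same arm.

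**Working it through.** The plan gives no figure to reproduce: no sample size, event count or healing rate. The check applies the SAP's rules to a made-up arm.

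**Inputs.** Arm of 12 (protocol, Randomization). Event time is the actual day; completers are censored at 42 (SAP). Visit 8 falls on Days 40 to 44 (protocol Section 8). Assumed for illustration: healings first seen on Days 14, 21, 28 and 44, and 8 completers not healed. Crude healing is 4/12 = 33%.

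**Formula.** S(t) = product of (1 − d/n) over event times, with d events among n at risk. Estimated healing is 1 − S.

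**Through Day 28.** S = (11/12)(10/11)(9/10) = 9/12 = 0.75, so 25% healed.

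**After Day 28, by reading:**
- *Visit 8 healings count, times as written.* The 8 non-healed subjects leave at 42. On Day 44 one subject is at risk and one heals: S = 0.75 × (1 − 1/1) = 0. The curve shows 100%, with a median of 44 days.
- *Treatment Phase healings only, late healer censored at 42.* No further event: 25%.
- *Treatment Phase healings only, late healer left out.* S = (10/11)(9/10)(8/9) = 8/11, so 3/11 = 27%.
- *Visit 8 healings count, strict cut at Day 42.* The Day 44 healing is dropped: 25%.
- *Visit 8 healings count, both times on the nominal day (42).* Nine are at risk and one heals: S = 0.75 × 8/9 = 0.667. The curve shows 33%, equal to the crude figure, and the median is not reached.

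Had the last healing been seen on Day 40, 41 or 42, the rules as written would also give 33%, because the non-healed completers are still at risk. The jump arises only on Days 43 and 44.

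**Exception.** If a non-completer is censored later than the late healing, the curve stays below 100%. Suppose the last healing is on Day 43 and one of the eight is an early terminator censored on Day 44. Two are then at risk: S = 0.75 × 1/2 = 0.375, or 63% healed.

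**Would censoring at the actual Visit 8 date be enough?** Take an arm of 12 with 2 healed on Day 21, 1 healed at Visit 8 and 9 not healed (crude 3/12 = 25%).
- Healing on Day 43 with 4 at risk: S = (10/12)(3/4) = 0.625, or 37.5%.
- Healing on Day 44 with one other subject seen that day: S = (10/12)(1/2) = 0.417, or 58.3%.
- Healing on Day 44 with nobody else seen that day: 100%.

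This reduces the artefact but does not remove it.

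**Log-rank test, if run.** Combined active 24 against placebo 8; 4 and 1 healed on Day 21; 3 active healings at Visit 8. Dated Day 42, the expected active count is 5 × 24/32 + 3 × 20/27 = 5.97 against 7 observed, and chi-square is 0.78. Dated Day 43, nobody on placebo is at risk, the expected count is 3.75 + 3 = 6.75, and chi-square is 0.08. Late healings add nothing here; they do not inflate the test.

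**The case against.** **The jump needs several interpretive steps.** The analyst must set aside the Treatment Phase wording, accept Day 43 or 44 as within six weeks, and decide that the SAP section headed "Visit window data including study endpoints" does not assign Visit 8 to its nominal day. This stands: the jump is conditional. A reader might infer that the SAP as written will produce a 100% curve, and the documents do not support that. But the readings that avoid it through the Treatment Phase limit or a Day 42 cut lose Visit 8 healings from a six-week curve. The nominal-day reading would be harmless, yet the visit-window section does not say that event times are reset, and the footnote uses dates.

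**A 28-day restriction may be deliberate.** The protocol's endpoint heading and its description of Visit 7 support this. Section 5.5 and the SAP's six-week outputs oppose it. The matter is unsettled, so the fix should not choose the endpoint for the sponsor.

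**A reader might infer that a false 100% is likely.** The documents give no healing rate and no spread of Visit 8 dates. Assuming a constant hazard, complete follow-up and 10% to 40% healed by Day 42, the chance for one arm of 12 runs from about 2% to 45%. The low end puts 80% of Visit 8 dates on Day 42 and adds a Day 35 visit. The high end has dates uniform over Days 40 to 44 and no visit after Day 28 until Visit 8. That range reflects the assumptions, not the trial.

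**The artefact would be seen.** The crude percentage healed is reported alongside, so a final step with one subject at risk would stand out. This stands and limits the harm.

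**Conclusion.** The point holds as a minor one. The SAP leaves the status of Visit 8 healings open and puts events and completer censorings on different clocks. The mismatch is in the text and depends on no assumption. The worked arm shows its possible size: 100%, 25% or 27% under the stated rules, against 33% crude. The 100% figure requires that Visit 8 healings count, that one is first seen on Day 43 or 44, and that no non-completer is censored later. How often that would occur cannot be derived from the documents.

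The effect is confined to the secondary time-to-heal plot and summaries and, if it is run, the conditional log-rank test, which would lose information from late healings. The primary safety endpoint, the crude percentage healed and percentage area reduction are not affected. A reader might infer that the trial's main conclusions are at risk; nothing in the documents supports that.

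**What to change.** In the SAP section on days to healing, state which healings are events and use the same horizon for events and censoring.

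- **If the six-week analysis is intended:** count healings through Visit 8, set both event and censoring times to the nominal visit day (Visit 8 = Day 42), and say so in the visit-window section.
- **If a 28-day endpoint is intended:** censor at Day 28 and relabel the six-week time-to-heal output. Use nominal days here too, because Visit 7 has the same two-day window.

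Censoring at the actual Visit 8 date is not a sufficient substitute. Showing the final Kaplan-Meier estimate beside the crude percentage healed gives a simple check.

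The cost is SAP wording only. Nominal days lose up to 2 days of timing detail, which matters little when healing is dated by the visit at which it is first seen.

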#### Randomization:

Randomization will be conducted to a ratio of 3:1 (active: placebo). All qualified subjects will be enrolled and randomized in two sequential Cohorts of 16 each, Cohort 1 to either Nu-3 gel at 5% or to placebo gel, and Cohort 2 to either 10% Nu-3 gel or to placebo gel. The two cohorts will be enrolled sequentially, each with 12 active and 4 placebo subjects, and safety will be evaluated by the independent Data Monitoring Committee (DMC) before proceeding to the next Cohort. At the completion of Cohort 2, the DMC will review all data and make a recommendation as to the appropriate dose for the next study.

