#### General

Descriptive statistical methods will be used to summarize the data from this study. These include number of subjects (n), mean and standard deviation (SD) for continuous variable data (medians and IQR [interquartile range] values will be given when the distribution of variable values is non-normal), and frequencies and percentages for categorical variable data. There will be no hypothesis testing performed. All data collected during the study will be reported and analyzed.

Unless specified otherwise, all statistical testing will be two-sided and performed using a significance (alpha) level of 0.05.

All statistical analyses will be conducted using PASW 27 (SPSS; IBM).

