#### **Sample Size Calculations**

Since this is a pilot study focusing primarily on safety, no sample size calculations will be done. Based on general experience with phase 2a trials, it is planned to enroll 32 subjects (24 active and 8 placebo).

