## Randomization

Subjects eligible for the study after screening and run-in will be randomized 3:1 to bisphosphocin Nu-3 gel and SOC or placebo gel SOC.

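### The ITT time-to-heal curve censors deaths and early-leaving ulcer removals at exit, as if those ulcers could still heal, although the SAP scores them as not healed

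*SAP*

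**What the plan says.** The SAP defines the outcome of an unhealed early leaver in two places.

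- **Days to Index Ulcer healing.** Every subject without a healing event is right-censored: completers at 42 days, early leavers at "Time of the early termination date of randomization for those subjects who withdraw or terminate early from the study (i.e. the censored time". Neither death nor amputation is named. The phrase is garbled and presumably means days from randomization to early termination.
- **Missing data.** Rule (a) reads "If an event removes the index ulcer, such as an amputation, the outcome will be scored as not healed". Rules (b) and (c) score death and withdrawal the same way. Rule (d) bases the remaining unhealed ulcers in the drug groups on outcomes in the SOC group.

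The Analysis section reports the number and percentage healed by 6 weeks. Beside it comes "Time to heal within 6 weeks (summary time to heal statistics by treatment group) using Kaplan-Meier method", plotted as one minus survival. A log-rank test follows only if the two doses' healed percentages lie within 10% of each other and a power calculation on combined active versus placebo reaches 80%.

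No competing-event rule is given. Nothing says whether the Missing data scoring carries into the curve. Table 2 (Patient Populations) ticks withdrawn, died or lost subjects for the ITT and Safety populations only.

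**The concern.** Censoring at exit assumes that the ulcer would have gone on healing at the rate of those still under observation. After death, or after the index ulcer has been removed, that cannot be so. The SAP recognises this in its percentage and then drops it in the curve. Two healing results for the same ITT arm can therefore disagree, with the curve the more favourable. If such losses are uneven between arms, the comparison can tilt towards the arm with more of them.

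Supporting dose selection is a secondary objective, and the DMC reviews all data to recommend a dose. With 12 subjects per dose, one ulcer is 1/12 = 8.3 percentage points, so a few exits matter.

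**Working it through.** **Inputs from the documents.** The SAP states that "it is planned to enroll 32 subjects (24 active and 8 placebo". The protocol's Randomization section has two cohorts, "each with 12 active and 4 placebo subjects", and 2 × (12 + 4) = 32 = 24 + 8. Post-baseline visits fall on Days 7, 14, 21, 28 and 42. There is no planned figure to reproduce: the SAP says "no sample size calculations will be done" and gives no rate of healing, death, amputation or withdrawal. All such rates below are assumptions.

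**The two rules side by side (ITT).**

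| Subject, not healed | Healed percentage | Curve |
|---|---|---|
| Dies before Day 42 | Not healed | Censored at exit |
| Ulcer removed, leaves early | Not healed | Censored at exit |
| Ulcer removed, completes Day 42 | Not healed | Censored at 42 days (consistent) |
| Other withdrawal | Not healed | Censored at exit |

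The first two rows are an inference, because the time-to-heal definition names neither event. A death necessarily ends participation early, so the early-termination rule is the only one that fits it.

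**Size in one arm.** The curve at Day 42 is 1 − Π(1 − d/n), where d is the number healing and n the number at risk at each healing time. Assume 12 subjects, with healing at Days 14, 21, 28 and 42, and L exits at Day 7. The product telescopes to (8 − L)/(12 − L), so the curve reads 4/(12 − L). For L = 3 it is 8/9 × 7/8 × 6/7 × 5/6 = 5/9, giving 44.4%.

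| Exits at Day 7 | Curve as written | Exits kept unhealed to Day 42 |
|---|---|---|
| 0 | 4/12 = 33.3% | 33.3% |
| 1 | 4/11 = 36.4% | 33.3% |
| 2 | 4/10 = 40.0% | 33.3% |
| 3 | 4/9 = 44.4% | 33.3% |

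**Timing.** Four exits at Day 7 give 4/8 = 50.0%. The same four at Day 20, 27 or 28 give 47.6%, 44.4% or 40.0%. If all exits follow the last healing, the curve stays at 33.3%. For the same subjects the curve is never below the healed percentage, and it is above it whenever an exit precedes a later healing.

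**Between arms.** Exits are again at Day 7.

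- 3 of 12 healed with 4 exits reads 3/8 = 37.5%, above an arm with 4 of 12 healed and no exits (33.3%). With 3 exits it is 3/9 = 33.3%, and with 2 it is 3/10 = 30.0%, so the reversal needs heavy loss.
- Combined active 8 of 24 healed with 0, 4 or 8 exits, against placebo 2 of 8 with none: the active curve reads 33.3%, 40.0% or 50.0%, and the log-rank p is 0.65, 0.46 or 0.26. With exits kept unhealed to Day 42, p stays at 0.65.

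**Does the curve always rise?** A large simulation took one third of ulcers healing and 0, 10, 20 or 30% lost. If losses fall only on ulcers that would not heal, the curve reads about 33, 35, 38 or 42%. If losses are independent of healing, it stays at 33%, and the scored percentage falls to 32, 30 and 28% at the three non-zero loss rates.

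**Reach into testing.** The SAP says "all statistical testing will be two-sided and performed using a significance (alpha) level of 0.05". At that level, with 24 against 8, the 80% condition needs at least 12/24 healed against 0/8, 16/24 against 1/8, 19/24 against 2/8 or 22/24 against 3/8. The condition uses healed proportions, while the test would use censored times.

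**The case against.** The strongest reply is that pairing a responder percentage that counts leavers as failures with a curve that censors them is common practice. For ordinary withdrawals this stands. Their ulcers may still heal, so 4/12 is then an imputation and not the truth. The independent-loss simulation shows that in that case the scored percentage is the one that misleads. The protocol does allow withdrawal for safety (section 10.2), for clinical deterioration (section 11.3) and after repeated non-permitted debridement (Appendix 4), so some withdrawals will be informative. That supports a sensitivity analysis, but it does not show that censoring withdrawals is wrong.

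A reader might infer three stronger things that the documents do not support.

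- **That an arm losing more ulcers will show a higher healing curve.** This depends on timing and on which ulcers are lost. If losses are spread evenly the distortion shrinks: 3 of 12 active and 2 of 8 placebo lost before any healing gives 4/9 − 2/6 = 11 points, against 4/12 − 2/8 = 8 as scored. With the three active losses and none in placebo, it is 4/9 − 2/8 = 19 points.
- **That gangrene and osteomyelitis lead to censoring.** Both documents make them reasons to pause treatment. Nothing censors a subject at a pause, and protocol section 10.1 asks for visits to continue after consent to treatment is withdrawn.
- **That every amputee is affected.** One who completes Day 42 is already handled consistently.

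Reach is also limited. The modified ITT and per-protocol populations leave these subjects out, and eligibility (Wagner grade 1, no suspected bone infection, life expectancy above 6 months) should keep such events few.

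**Conclusion.** The inconsistency is real for ITT subjects who die, or whose ulcer is removed and who leave before Day 42. For them, censoring at exit contradicts both the SAP's own scoring and the fact that the ulcer can no longer heal. The curve then exceeds the healed percentage whenever such an exit precedes a later healing. With 4 of 12 healed, 1 to 3 early exits add about 3, 7 or 11 points; with exits after the last healing the effect is nil. These sizes rest on assumed healing and loss, since the documents give neither.

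The consequence is confined to a secondary, mainly descriptive endpoint and to a log-rank test that will seldom run. The primary analysis of treatment-emergent adverse events is untouched. The change is still worth making, because the plot and the time-to-heal summaries are produced unconditionally.

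**What to change.** In the SAP's Days to Index Ulcer healing section:

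1. Treat death and removal of the index ulcer as competing events. Either keep these subjects unhealed in the risk set to Day 42, or report an Aalen-Johansen cumulative incidence of healing. Name one, since the two coincide only when there is no other censoring before Day 42. Apply it whether or not the subject attends Day 42, and use the same coding if the log-rank test is run.
2. For other withdrawals, censoring at exit may stay. State that the curve and Missing data rule (c) differ for them, and show a version with withdrawals unhealed to Day 42 as a sensitivity analysis.
3. Correct the garbled censoring time to days from randomization to early termination.

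The Day 42 curve need not equal the healed percentage after this, because withdrawals are treated differently and rule (d) may alter other outcomes. A note beside the plot should say so.

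The cost is a few lines of SAP wording, a recode of censoring times and one extra sensitivity run, with no new data.

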# 10.3. Lost to Follow-Up

A subject will be considered lost to follow-up if he or she repeatedly fails to return for scheduled visits and is unable to be contacted by the study site.

The following actions must be taken if a subject fails to return to the clinic for a required study visit:

- The site must attempt to contact the subject and reschedule the missed visit as soon as possible and counsel the subject on the importance of maintaining the assigned visit schedule and ascertain whether or not the subject wishes to and/or should continue in the study.
- Before a subject is deemed lost to follow up, the investigator or designee must make every effort to regain contact with the subject (where possible, 3 telephone calls and, if necessary, a certified letter to the subject's last known mailing address or local equivalent methods). These contact attempts should be documented in the subject's medical record.
- Should the subject continue to be unreachable, he/she will be considered to have withdrawn from the study with a primary reason of lost to follow-up.

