# **Brief Trial Description**

This study is a phase 2a, multi-center, double-blind, placebo-controlled, dose-escalating, parallel group, randomized controlled trial designed to evaluate the safety and tolerability of topically applied bisphosphocin NU-3 gel to clinically non-infected Wagner grade 1 diabetic foot ulcers (DFUs).

Two weeks after screening, subjects will be randomized 3:1 to bisphosphocin Nu-3 gel and standard of care (SOC) or placebo gel and SOC to treat Wagner 1 DFUs. Major inclusion criteria will be DFUs between 1.0 and 10 cm^2 initial area and having no wound ischemia.

Subjects will be seen weekly until 6 weeks after randomization unless the subject's wound healed, or the subject is withdrawn or lost to follow-up (i.e., early termination). The bisphosphocin Nu-3 or placebo gel will be applied starting on the day of randomization for 4 weeks twice daily. The study will be executed in two phases: cohort 1 and cohort 2, in which the doses for the intervention group will be 5% or 10% Nu-3 gel.

SOC in this study will be offloading of the DFU using a removable cast walker provided to the subject, appropriate sharp or surgical debridement (note: there will be several rules pertaining to prohibition on certain visits and degree of debridement), and infection management post-randomization as deemed appropriate by the investigator. Primary dressings will be Mepitel (or equivalent), Tegaderm, and padding/Coban Lite 2- layer dressing.

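### The censoring date for subjects lost to follow-up without an exit examination is undefined, and its natural reading falls after the last ulcer examination (minor)

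*SAP*

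**What the plan says.** - **Event date.** SAP, Date of healing: "The date of healing is defined as the date of the first assessment of index ulcer healing". Healing enters the data only when someone examines the ulcer.
- **Censoring, completers.** SAP, Days to Index Ulcer healing: "42 days if the subject completes the study".
- **Censoring, early leavers.** Same section: "Time of the early termination date of randomization for those subjects who withdraw or terminate early from the study (i.e. the censored time"). Read literally this is not a date. The footnote formula for days to healing subtracts the randomization date, so the likely intent is early-termination date minus randomization date.
- **Who is covered.** The SAP's Brief Trial Description counts a subject as an early leaver if "the subject is withdrawn or lost to follow-up (i.e., early termination"). Protocol 10.3 agrees: an unreachable subject "he/she will be considered to have withdrawn from the study with a primary reason of lost to follow-up".
- **When lost status arises.** Protocol 10.3: "A subject will be considered lost to follow-up if he or she repeatedly fails to return for scheduled visits" and cannot be contacted. Contact attempts come first: "where possible, 3 telephone calls and, if necessary, a certified letter".
- **Exit examination.** Protocol section 8 (Early Termination Visit) and the schedule in section 9 include a visual ulcer examination and digital imaging for subjects who attend that visit.
- **Use of the times.** SAP, Analysis: a Kaplan-Meier summary of time to heal within 6 weeks, with a logrank test only if two preconditions are met.

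**The concern.** Events are dated by examination, while censoring of early leavers is dated by a termination date that neither document ties to an examination. If the second date is later than the first, the subject counts as at risk and unhealed on days when a healing could not have been seen. The denominator grows and the numerator cannot, so the Kaplan-Meier healing probability is too low in any arm that loses subjects this way. With 12, 12 and 8 subjects per group, a single loss can shift the estimate. Sites that date termination differently (up to five are planned) would also produce different curves from the same clinical course.

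**Working it through.** **No figure to reproduce.** The documents give no expected healing rate, loss rate or power for this endpoint. All healing, loss and lag values below are assumptions.

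**Step 1: who is affected.** If an early-termination visit is attended, the ulcer is examined on that date, so termination date and last examination coincide. Only subjects with no exit examination can be affected.

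**Step 2: the gap for a lost subject.** Post-baseline visits fall on Days 7, 14, 21, 28 and 42. If repeated failure to return means at least two missed visits, a subject last seen on Day 14 cannot be declared lost before about Day 28. One last seen on Day 21 cannot be declared lost before about Day 42, and so would be carried through Days 28 and 42 like a completer.

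**Step 3: direction.** Estimated healing is 1 − ∏(1 − d/n), with d healings and n at risk at each event day. Keeping unexamined subjects in n raises each factor, so estimated healing stays the same or falls.

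**Step 4: size in one arm.** Assume three healings (Days 21, 28, 42), last examination of the lost subjects on Day 14, and termination recorded on Day 28. By the usual convention, a subject censored on an event day is still at risk that day.

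| Arm size | Lost | Censored at last examination | Censored at termination date | Difference (points, unrounded values) |
|---|---|---|---|---|
| 8 | 1 | 1 − (6/7)(5/6)(4/5) = 42.9% | 1 − (7/8)(6/7)(4/5) = 40.0% | 2.9 |
| 8 | 2 | 1 − (5/6)(4/5)(3/4) = 50.0% | 1 − (7/8)(6/7)(3/4) = 43.75% | 6.25 |
| 12 | 1 | 1 − (10/11)(9/10)(8/9) = 27.3% | 1 − (11/12)(10/11)(8/9) = 25.9% | 1.3 |
| 12 | 2 | 1 − (9/10)(8/9)(7/8) = 30.0% | 1 − (11/12)(10/11)(7/8) = 27.1% | 2.9 |

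**Step 5: sensitivity to the layout.** The shift is largest when every healing falls inside the unobserved gap.
- Arm of 8, two healings on Day 28, one subject last seen Day 14 and declared lost Day 35: 2/8 = 25.0% against 2/7 = 28.6%.
- Arm of 12, two healings on each of Days 21 and 28, two subjects last seen Day 7 and declared lost Day 30: 4/12 = 33.3% against 4/10 = 40.0%.
- The same arm with lost status assigned between Days 22 and 27: 1 − (10/12)(6/8) = 37.5% against 40.0%.

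**Step 6: average size.** A simulation of 200,000 subjects assumed an equal healing chance at each visit, loss unrelated to healing, last examination on Day 0, 7 or 14, and termination dated at the second missed visit. With true Day-42 healing of 30%, last-examination censoring returned about 30% throughout. Termination-date censoring gave 29.5%, 28.8%, 27.8% and 26.4% with 5%, 10%, 20% and 30% lost. Over the same range of loss it gave 19.7% to 17.6% for true healing of 20%, and 49.4% to 44.6% for 50%.

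**Step 7: reach into the logrank test.** One precondition is at least 80% power for combined Nu-3 against placebo. With 24 against 8, two-sided alpha 0.05 and the normal approximation, power is Φ[(|p1 − p2| − 1.96·√(p̄(1 − p̄)(1/24 + 1/8))) / √(p1(1 − p1)/24 + p2(1 − p2)/8)].
- 19/24 against 2/8: Φ[(0.542 − 0.380)/0.174] = Φ(0.93), about 82%.
- 16/24 against 1/8: Φ[(0.542 − 0.399)/0.151] = Φ(0.94), about 83%.

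One fewer healing in the active group drops each to about 74%. The test therefore runs only when the observed difference is around 54 points.

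**The case against.** **The documents never say that a lost subject is censored on the day of declaration.** Protocol 10.3 sets conditions for lost status but assigns no date, and wherever early termination is described operationally it is a visit with an ulcer examination. If the sponsor dates termination at the last attended visit, the bias is zero. This stands. A reader might infer that the SAP censors every early leaver later than the last examination; the text does not support that. What remains is an undefined date whose most natural reading is unfavourable.

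**The SAP already has a conservative convention.** Under Missing data, a withdrawn subject with a missing healing outcome is scored as not healed. The later-censored figures in the two extreme layouts, 2/8 and 4/12, are exactly the proportions that this convention gives. But the rule scores a binary outcome and sets no censoring time, while the time-to-heal section treats the same subjects as right-censored. It does not settle the question, though it does mean that the two summaries can differ after the fix.

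**The shift is small against the imprecision.** Exact 95% intervals are about 3% to 65% for 2/8 and 10% to 65% for 4/12. A reader might infer that a few lost subjects could change the trial's conclusions, or that one arm is favoured. Neither is supported: the primary endpoint is safety, the logrank test needs a very large difference before it runs, and nothing in the documents suggests unequal loss between groups.

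**Conclusion.** The point holds in limited form and is minor. It rests on three assumptions: that the termination date of a lost subject is the day lost status is assigned, that at least one subject is lost without an exit examination, and that another subject in the arm heals in the gap. Then estimated Day-42 healing is lowered by roughly 1 to 3 points with one loss in an arm of 12 or 8, and by about 3 to 6 points with two. Layouts that put every healing inside the gap give slightly more.

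Calling this a bias, and last-examination censoring its cure, also assumes that loss is unrelated to healing. If lost subjects tend to heal less, neither rule is exact. The effect is confined to a secondary efficacy summary and a test that may not be run.

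**What to change.** Replace the second censoring bullet under Days to Index Ulcer healing, which needs rewording anyway, with:

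*For subjects who withdraw, terminate early or are lost to follow-up without healing: date of the last index-ulcer assessment (including an early-termination visit, if attended) minus date of randomization.*

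Add one sentence under Missing data: the scoring of withdrawn subjects as not healed applies to the proportion healed and does not set the Kaplan-Meier censoring time, so the two figures may differ slightly.

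The cost is two sentences in the SAP before database lock. The ulcer is examined at every scheduled visit, so the dates are already collected, and nothing changes for subjects who attend the exit visit.
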